### **12.8 Trial Documentation and Storage**

The investigator/institution should maintain the trial documents in a comprehensive and centralised filing system that is suitable for inspection by representatives of the Sponsor and regulatory authorities. The investigator/institution should take measures to prevent accidental or premature destruction of these documents.

Essential documents as defined by ICH GCP include the signed protocol and any amendment(s), copies of the completed CRFs, signed informed consent forms from the parent(s)/legal guardians of all patients for whom consent was obtained, hospital records and other source documents, IEC approvals and all related correspondence including approved documents, drug accountability records, site delegation lists and curriculum vitae, trial correspondence and a list of the patients' names and addresses.

The principal investigator must retain copies of all essential documents for the period specified by ICH GCP and by applicable regulatory requirements.

The principal investigator will inform the Sponsor of the storage location of the essential documents and must contact the Sponsor for approval before disposing of any of these documents.

It is the responsibility of the Sponsor to inform the investigator/institution as to when these documents no longer need to be retained. The Sponsor should be informed immediately by the investigator/institution of any change concerning archiving facilities.

### **12.9 End of trial**

For administrative and safety reporting purposes the end of the trial will be defined as 14 days after the last patient completes treatment in My-CRA Month 2. This provides for a single and conservative definition.

### **12.10 Publication Policy**

The Sponsor will prepare a written clinical trial report according to ICH guidelines to summarise the trial following completion of the analysis.

Investigators may not submit trial information for publication without prior consultation and written approval from the Sponsor. However such approval should not be unreasonably withheld.

## **13 ADMINISTRATIVE OBLIGATIONS**

### **13.1 Source Data**

All relevant trial data will be recorded in the CRF. Where relevant data already exists on other source documents such as laboratory reports or ECGs, the information required will be transcribed into the CRF. All other data will be directly written into the CRF.

### **13.2 Monitoring**

Routine monitoring visits will be made by the monitors designated by the Sponsor to check compliance with the protocol, the completeness, accuracy and consistency of the data, and adherence to GCP.

The principal investigator must ensure that CRFs are completed in a timely manner and must allow periodical access to CRFs, patient records, drug logs and all other trial-related documents and materials. The frequency of monitoring visits will be determined by factors such as trial design and the site enrolment requirements. For this trial, monitoring visits will usually occur a few weeks after a patient is recruited and completes My CRA-Month 2, at an individual site.

The investigator will agree to provide the monitor direct access to the patients' source data, which may exist in the form of hospital records, patient files and notes, and laboratory assessment reports and results.

### **13.3 Quality Control and Quality Assurance**

Appropriately qualified and trained staff will be involved in this trial. Staff at the investigational site will be instructed in the conduct of the trial according to this protocol.

In order to check the compliance of the trial regarding GCP, audits may be carried out by a quality assurance representative. The investigator will provide access to authorised persons during regulatory authority inspections or Sponsor audits.

### **13.4 Data Collection and Management**

A CRF will be completed for each patient who enters the trial. The CRFs will be printed and the original CRFs will be collected by the Sponsor or their delegate – a photocopy will be retained at the site.

The CRFs should be completed legibly in English with a black ball-point pen. Errors should be crossed by a single line but not obliterated, and the change initialled and dated by the investigator or designee. The use of correction fluid or tape is not allowed. The investigator will sign and date at the indicated places in the CRF. This signature will indicate a thorough inspection of the data on the CRF has been made, and will certify the contents of the form.

CRFs will be completed promptly and submitted to the monitor in person for checking and collection. When changes to CRF data are necessary following removal of the original CRF from the trial site these changes will be documented on data clarification/resolution forms which will be signed by the investigator.

The data will be entered into a validated database. TASK Applied Science Pty Ltd will be responsible for data processing, in accordance with the Sponsor or Sponsor's delegated service provider's data management procedures. Database lock will occur once quality assurance procedures have been completed. Nova will send results to other South Africa. Patients information sheets will include details that cover data being sent outside of the UK, and the consent form will cover a request for consent to do so.

Data items from the CRF will be entered centrally into the trial database by Data Management using double data entry, with verification upon second entry. Concomitant medication entered onto the database will be coded using the WHO Drug Reference List. Coexisting diseases and AEs will be coded using the Medical Dictionary for Regulatory Activities (MedDRA). Laboratory samples will be processed and results sent to Data Management.

### **13.6 Adherence to the Protocol**

Protocol violations are any deviations from the procedures outlined in this document, for example, missed evaluations, incorrect timing of evaluations, non-compliance with IMP and intake of prohibited medications. It is the investigator's responsibility to make all reasonable efforts to avoid protocol violations in order to avoid possible exclusion of the patient from the trial and/or analyses.

All protocol violations will be reported immediately to the Sponsor and any action required, for example, discontinuation of the patient will be discussed. Evaluability of the patient(s) concerned will be performed by the Sponsor prior to the statistical analysis.

Any deviation from the protocol that has not been approved by The Sponsor and the IEC could result in a discontinuation from the trial of the site involved.

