### **3.2 Type of trial**

This is an open label, randomised, multiple dose, cross-over relative bioavailability and pharmacokinetics trial of oral 13–CRA liquid administered to patients aged from 0-< 21 years. The decision to initiate 13-CRA therapy will be taken independently of this trial protocol. The trial will be conducted in patients who are attending the hospital for treatment for neuroblastoma requiring at least two cycles of 13-CRA. 13–CRA will be prescribed to patients according to the locally approved treatment protocols at a dose of 200mg/m^2/day for both test and reference product. Oral 13–CRA is administered for NBL (this is usually at a dose of 160mg/m^2) for 14 days, every 4 weeks, for 6 months, however where the dose is extracted from capsules this dose

is increased to 200mg/m^2. In this trial the dose of 13-CRA will be 200mg/m^2 as patients able to swallow the capsules will not be recruited to the trial. Patients with a body weight of ≤12kg will receive a dose of 160 mg/m^2. Patients who require their dose through a nasogastric tube or gastromy will be included in the trial, this will be recorded in the case record form.

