### **11.3 Statistical analysis**

#### **11.3.1 Analysis Populations**

The primary trial population will be the Pharmacokinetic (PK) population. The PK population will include those patients who had at least one successful blood sample taken and complete the trial without significant protocol deviations/violations which are likely to affect the determination of the pharmacokinetic parameters. Further details on what is deemed a significant protocol deviation/violation will be documented in the Statistical Analysis Plan. This population will be used for the analysis of the primary variable.

Safety data will be presented for the Safety population, that is, it will include all patients who received trial medication.

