7.2 Randomisation

Prior to the initiation of the trial 13-CRA, patients will be randomised to receive either liquid or extracted capsule formulation in “My –CRA month 1”. The patients will then cross-over to the alternative formulation in “My-CRA month 2”. After the trial if a patient requires additional cycles of 13-CRA, the patient will revert to standard 13-CRA therapy i.e. extracted capsules according to local practice.

Randomisation will be done centrally by Nova according to a randomisation list generated by the trial statistician, investigators will email (or telephone) Nova to receive randomisation details, this will be confirmed by email as “liquid first” or “extracted capsules first”, pharmacy contacts will also be notified.

8 Major Protocol Deviations

Protocol violations are any deviations from the procedures outlined in the protocol, for example, missed evaluations, incorrect timing of evaluations, non-compliance with investigation medical product (IMP) and intake of prohibited medications. It is the investigator’s responsibility to make all reasonable efforts to avoid protocol violations in order to avoid possible exclusion of the patient from the trial and/or analyses.

Major protocol deviations are defined as those deviations from the study protocol that may have the ability to impact the study results.

Major protocol deviations include (but are not limited to):

- Deviation from inclusion/exclusion criteria
- Withdrawal criteria met during the study but patient was not withdrawn
- Missed evaluations
- Incorrect timing of evaluations
- Prohibited concomitant medications
- Non-compliance with IMP

Where possible; major deviations will be programmatically generated. Listings of concomitant medications will be provided to the sponsor for review to identify prohibited medications prior to database freeze.

Major protocol deviations will result in exclusion from the pharmacokinetic population if they are considered likely to affect the determination of the pharmacokinetic parameters.

9 Analysis Populations

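### Neither document stops those judging evaluability from seeing 13-CRA concentrations first, and two conflicting rules define the primary PK analysis set

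*Protocol*

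**What the plan says.** **Who decides, and when.** Protocol 13.6: "Evaluability of the patient(s) concerned will be performed by the Sponsor prior to the statistical analysis". Protocol 3.2 describes the design: "This is an open label, randomised, multiple dose, cross-over relative bioavailability and pharmacokinetics trial". Under Protocol 6.1 the sponsor itself gives each site the treatment sequence, so it knows which cycle was liquid and which was capsule.

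**On what criterion.** Protocol 11.3.1 limits the PK population to patients with at least one successful sample who "complete the trial without significant protocol deviations/violations which are likely to affect the determination of the pharmacokinetic parameters", and leaves the meaning of a significant deviation to the SAP. SAP section 8 introduces its list with "Major protocol deviations include (but are not limited to". The list includes missed and mistimed evaluations, with no tolerance window. The section then says: "Major protocol deviations will result in exclusion from the pharmacokinetic population if they are considered likely to affect the determination of the pharmacokinetic parameters". It does not say who does the considering or which data they may consult.

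**Order of events.** Protocol 11.3.3 places the review of deviations, agreement of the populations and database lock before the statistical analyses. Protocol 13.4 says of the assay results only: "Laboratory samples will be processed and results sent to Data Management".

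**A second inclusion rule.** Protocol 3.1 and 8.3 put every patient with at least one PK sample into the PK analysis. Protocol 8.1 adds that data up to withdrawal, PK samples included, will be used unless the family objects.

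**Scope.** SAP sections 2 and 12 place the population PK analysis outside the SAP.

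**The concern.** Relative bioavailability is a primary parameter, and it is to come from perhaps 12 to 18 patients. If the people who decide exclusions know each patient's sequence and can also look at the concentrations, they can recognise a patient whose liquid and capsule levels disagree with the rest without fitting any model. A criterion that turns on what is considered likely to affect PK then gives no protection, even when it is applied in good faith. Holding the decision before the analysis is not the same as holding it before the data are visible.

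The conflict between the two inclusion rules adds a second choice: whether exclusions are allowed at all in the population PK analysis. What is at stake is the credibility of the primary ratio, because a reader could not tell whether the analysis set was fixed independently of the results.

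**Working it through.** The plan states no power calculation, target ratio or variance, so there is no planned figure to reproduce. The check has two parts.

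**1. The text, side by side**

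| Question | What the documents give |
|---|---|
| Who judges evaluability? | The sponsor (Protocol 13.6); SAP 8 names no one |
| Is treatment known to the decision-maker? | Yes: open label, sequences issued by the sponsor (Protocol 3.2, 6.1) |
| Is the criterion fixed in advance? | Open-ended list, no thresholds (SAP 8) |
| Is the decision before analysis? | Yes (Protocol 11.3.3, 13.6) |
| Is the decision before sight of concentrations? | Not stated; no embargo, restricted access or blinded review described (Protocol 13.4) |
| Who is in the PK analysis? | Everyone with a sample (Protocol 3.1, 8.3), or only completers without significant deviations (Protocol 11.3.1, SAP 9.1) |
| Does the SAP rule bind the population PK analysis? | Unclear, since that analysis is out of the SAP's scope (SAP 2, 12) |

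A patient who gives samples in cycle 1 and then withdraws is in the analysis under one rule and out under the other, with no deviation needed.

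**2. Scale of a selective exclusion (illustration)**

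From the documents: n = 12 and 18, the hoped-for range (Protocol section 11, SAP 7.1).

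Assumptions not in the documents: true ratio 1.00; within-patient CV of 30%, 40% or 50%; a simple mean of per-patient log(test/reference) in place of the mixed-effects model.

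SD of one patient's log ratio = √2 × √ln(1 + CV²). At CV 30% this is √2 × √ln(1.09) = 1.414 × 0.2936 = 0.415.

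In 100,000 simulated trials per setting, the patients with the lowest ratios were removed and the geometric mean ratio recalculated:

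| n | CV | lowest one dropped | lowest two dropped |
|---|---|---|---|
| 12 | 30% | 1.063 | 1.120 |
| 12 | 40% | 1.085 | 1.162 |
| 12 | 50% | 1.104 | 1.201 |
| 18 | 30% | 1.046 | 1.086 |
| 18 | 40% | 1.060 | 1.114 |
| 18 | 50% | 1.074 | 1.142 |

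Dropping two patients at random left the ratio between 0.999 and 1.001 in all six settings, so the shift comes from selecting on the result and not from losing patients.

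Against the standard error at CV 30%:

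- n = 12: SE = 0.415/√12 = 0.120. One dropped: ln(1.063) = 0.061, and 0.061/0.120 = 0.51 SE. Two dropped: ln(1.120) = 0.113, and 0.113/0.120 ≈ 0.95 SE.
- n = 18: SE = 0.415/√18 = 0.098. One dropped: ln(1.046) = 0.045, and 0.045/0.098 = 0.46 SE. Two dropped: ln(1.086) = 0.082, and 0.082/0.098 = 0.84 SE.

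**The case against.** **The order of events is already fixed.** Protocol 11.3.3 puts population agreement and lock ahead of analysis. This stands, and it narrows the point: exclusion after seeing an estimated ratio is ruled out. What it leaves open is sight of the raw concentrations.

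**Sponsor access is not shown.** A reader might infer that the sponsor's evaluators hold the concentration data. The documents do not say so. Protocol 13.4 sends results to Data Management and names a separate contractor for data processing, under procedures not included here. The gap is the absence of a bar, not evidence of access.

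**Few patients may be exposed to this judgement.** A reader might infer that missed or mistimed samples will be common and open many patients to exclusion. Nothing in the documents supports that. Only the 2 h and 6 h samples are mandatory, most others are taken where possible, and children under two have individually agreed times (Protocol 4.6). Precise times are recorded (Protocol 3.5) and the model is meant for sparse data (Protocol 11.1). Many absent or off-nominal samples would not be deviations.

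**Controls exist.** SAP 8 says that, where possible, "major deviations will be programmatically generated". Deviations are tabulated by sequence, and population allocation and concentrations are listed for all patients (SAP 11.1, 17.3). These controls identify deviations and make exclusions visible. They do not settle which flagged patients are excluded, or what the decision-maker knew.

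**The all-sample rule may govern.** If Protocol 3.1 and 8.3 prevail, no such exclusion arises in the population PK analysis. That is correct, but the documents do not say which rule prevails.

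**The shifts are worst cases.** They need the most extreme patients to have a qualifying deviation and to be dropped in one direction. One patient moves the estimate by about half an SE, not a full one. No acceptance limits for the ratio are stated, so no pass/fail decision is shown to turn on the shift.

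**Conclusion.** The point holds as a gap in procedure. A sponsor-made judgement, with treatment known and no thresholds, is ordered before the analysis but not before sight of the concentrations, and the primary analysis set has two incompatible definitions. The PK population could be influenced by the observed data.

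The documents do not support the further inference that it was. SAP section 16 shows that the text was written when the enrolled patients' ages were known. It does not show that concentrations were known then, or that any patient was excluded because of them.

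On size, the directional worst case is a shift in the ratio of about 6–10% (n = 12) or 5–7% (n = 18) for one patient, and about 12–20% or 9–14% for two. At CV 30% that is roughly half an SE and nearly one SE. These figures rest on the assumed CV of 30–50% and on a paired log-ratio standing in for the population model. They show scale and are not a forecast. The change is worth making because it is cheap and removes the doubt.

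**What to change.** 1. Reconcile Protocol 3.1 and 8.3 (and the use of pre-withdrawal data in 8.1) with Protocol 11.3.1 and SAP 9.1, so that one rule defines the primary PK analysis set.
2. State in Protocol 13.6 and 11.3.1 and in SAP sections 8 and 9 that deviations are classified and the PK population is signed off before 13-CRA concentrations are released, or by staff who have no access to them.
3. Put the same rule in whatever plan governs the population PK analysis. Because the SAP excludes that analysis from its scope, editing the SAP alone may not bind the estimate that matters.
4. Report the relative bioavailability estimate also for all patients with at least one sample, beside the primary set if the two differ.

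The cost is some wording, the timing of one review meeting and one extra model run. No additional patients, samples or visits are needed.

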### **13.7 Trial or site discontinuation**

The Sponsor may temporarily or permanently discontinue the trial at a single site or at all sites for safety, ethical, compliance or other reasons. If this is necessary, The Sponsor will endeavour to provide advance notification to the site(s) involved. If the site or trial is suspended or discontinued, the principal investigator will be responsible for promptly informing the IEC. Where required by local regulations, The Sponsor will be responsible for informing the IEC of trial or site discontinuation. In such cases, all trial data and unused investigational medicinal product must be returned to The Sponsor.

## **13.8 PERSONNEL RESPONSIBILITIES**

The trial will be conducted in accordance with the protocol, Good Clinical Practice and applicable regulatory requirements.

### **13.8.1 Investigator**

The investigator's responsibilities shall include but not be limited to:

- (i) adhering to the conduct of the trial as described in this protocol
- (ii) ensuring the accuracy and legibility of the CRFs and their security
- (iii) immediately reporting any serious adverse events to the Sponsor and, if appropriate, the Ethics committee
- (iv) adhering to the guidelines described in the Declaration of Helsinki and ICH Guideline for Good Clinical Practice and local regulatory requirements.
- (v) informing the patient's general practitioner that the patient is taking part in the trial, provided that the patient agrees to this contact. A copy of the correspondence should be filed in the Investigator Site File.
- (vi) Provide expert research input and advice relating to trial design and execution.
- (vii) Be responsible for the review and sign-off of the final report.

### **13.8.2 Clinical monitor**

The clinical monitor's responsibilities shall include but not be limited to:

- (i) verifying protocol adherence
- (ii) verifying the data on the CRFs with information in the patient's clinic notes and other source documents

- (iii) ensuring the trial documents such as the CRFs, protocol and any correspondence are maintained in a secure area
- (iv) reporting and discussing any problems with the investigators and reporting them to the Sponsor.

### **13.8.3 Sponsor**

As trial Sponsor's responsibilities shall include but not be limited to:

- (i) providing the principal investigator with all the necessary trial documents and trial supplies prior to trial initiation
- (ii) providing the investigator with updates on new developments regarding the trial drug
- (iii) sending the principal investigator financial reimbursement during the conduct of the trial according to a schedule agreed upon in the budget

## 15 APPENDICES

Appendix I	Trial schedule
Appendix II	Co-Investigator Signature sheet
Appendix III	Protocol Amendments

**APPENDIX I TRIAL SCHEDULE: EACH CYCLE**

Test	Pre trial	Day 1	Day 14	Day 15/16	End of trial  (Day 29)
Informed consent / assent 	x				
Medical history	x				
Concomitant medications	x	x	x		x
Physical Examination	x				
Pregnancy Test 	x				
Check for central line in situ	x	x			
13-CRA morning dose		x	x		
Pharmacokinetic blood samples 		x	x	x	
Vital signs for safety 		x	x		
Palatability 			x		
Oro-pharyngeal tolerability 		x	x		x
Adverse events / serious adverse events 		x	x		x

- 1 Parents/legal guardian will be asked to give informed consent to their child participating in the pharmacokinetic trial before 13-CRA is administered. Patients over the age of 7 years will be asked to give their assent to participate in the pharmacokinetic trial if it is deemed appropriate.
- 2 Pregnancy test for females of childbearing age, not more than 7 days prior to starting treatment (each cycle).
- 3 Up to five pharmacokinetic blood samples will be taken.
- 4 Systolic and diastolic blood pressure, pulse and body temperature at baseline (in older patients this will be following 5 mins rest in supine position).
- 5 Palatability assessment will be made at the 14 day visit. This will be done using a face to face survey.
- 6 Assessed at baseline and during the trial and follow up
- 7 On discharge from site or withdrawal from trial (AEs followed for up to 14 days later, if in diary card or if reported to research staff.

